**Events Meeting the AE Definition:**

- Any abnormal laboratory test results (haematology, clinical chemistry, or urinalysis) or other safety assessments (e.g. ECG, radiological scans, vital sign measurements), including those that worsen from baseline, considered clinically significant in the medical and scientific judgment of the investigator (i.e., not related to progression of underlying disease).
- Exacerbation of a chronic or intermittent pre-existing condition including either an increase in frequency and/or intensity of the condition.
- New conditions detected or diagnosed after informed consent signing (prior to study product administration) even though it may have been present before the start of the study.
- Signs, symptoms, or the clinical sequelae of a suspected drug-drug interaction.
- Signs, symptoms, or the clinical sequelae of a suspected overdose of either study product or a concomitant medication. Overdose per se will not be reported as an AE/SAE unless it is an intentional overdose taken with possible suicidal/self-harming intent. Such overdoses should be reported regardless of sequelae.
- The signs, symptoms, and/or clinical sequelae resulting from lack of efficacy will be reported as AE if they fulfill the definition of an AE. Also, "lack of efficacy" or "failure of expected pharmacological action" constitutes an AE.

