## **8 DISCONTINUATION OF STUDY INTERVENTION AND SUBJECT DISCONTINUATION/WITHDRAWAL**

### **8.1 Discontinuation of Study Intervention**

A subject may choose to discontinue or may be discontinued from the study intervention early at any time whilst still in the study at the discretion of the investigator for the following reasons related to safety, subject consent or a potential worsening of the risk / benefit assessment from the subject of remaining on the intervention:

- Adverse Event
- Lack of efficacy from the intervention
- Subject to be withdrawn from the study (see below - section 8.2)

If a subject is discontinued early from the intervention, the reason(s) for discontinuation and the associated date must be documented in the relevant section(s) of the eCRF. The subject should stay in the study and complete the remaining assessments unless they need to be withdrawn (see section 8.2).

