**Events NOT meeting the AE definition:**

- Any clinically significant abnormal laboratory findings (if applicable) or other abnormal safety assessments which are associated with the underlying disease, unless judged by the investigator to be more severe than expected for the subject's condition.
- The disease/disorder being studied or expected progression, signs, or symptoms of the disease/disorder being studied, unless more severe than expected for the subject's condition.
- Medical or surgical procedure (e.g. endoscopy, appendectomy) is not the AE. The condition that leads to the procedure is an AE (e.g. appendicitis).
- Situations where an untoward medical occurrence did not occur (social and/or convenience admission to a hospital).
- Anticipated day-to-day fluctuations of pre-existing disease(s) or condition(s) present or detected at the start of the study that do not worsen.

Property of Haleon - Confidential

May not be used, divulged, published or otherwise disclosed without the consent of  
 Haleon

Clinical Protocol Template, TMF-187821, v11.0. Parent SOP: **CCI**

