## 11.6 Withdrawal Due to an Adverse Event

Withdrawal due to AEs should be distinguished from withdrawal due to other causes, according to the definition of an AE noted earlier, and recorded on the appropriate AE eCRF page.

Property of Haleon - Confidential

May not be used, divulged, published or otherwise disclosed without the consent of  
 Haleon

Clinical Protocol Template, TMF-187821, v11.0. Parent SOP: **CCI**

When a subject withdraws because of an SAE, the SAE must be reported in accordance with the reporting requirements defined.

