## 7.4 Analysis Variables

### 7.4.1 Disposition

Subject disposition data are collected on the 'Study Termination' eCRF page. Subjects are recorded as "Completed", "Screening failure", or "Early withdrawal". The date of the disposition event, date of last application of study drug and, if applicable, the date of death is recorded.

If applicable, the primary reason for discontinuation may include any of the following:

- Adverse Event (with a drop down to specify the AE number);
- Death;
- Inclusion not met/ Exclusion criteria met;
- Lack of efficacy;
- Lost to follow-up;
- Non-compliance with study drug;
- Occurrence of pregnancy;
- Physician's decision;
- Protocol violation;
- Withdrawal of consent;
- Withdrawal due to no pain;
- Other (with a free text to specify).

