## 10.7 Safety Results

### 10.7.1 Adverse Events

#### 10.7.1.1 Brief Summary of Adverse Events

An Overview of AEs including but not limited to

- the number of subjects with at least one AE;
- the number of subjects with at least one pre-treatment AE;
- the number of subjects with at least one TEAE;
- the number of subjects with at least one Serious TEAE;
- the number of subjects who permanently discontinued Study Treatment due to a TEAE;
- the number of subjects with a TEAE related to study treatment;
- the number of subjects who had a TEAE with outcome of death
- the worst severity of any TEAE experienced by each subject with at least one TEAE

is summarized by treatment and overall, for the SAF in Table CCI [REDACTED]

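### Lack of efficacy counts as an adverse event, but no rule covers the ordinary non-responder, so headline AE counts can mix non-response with harm

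*Protocol*

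**What the plan says.** Protocol 11.1 treats lack of efficacy in two steps. The first is conditional: "The signs, symptoms, and/or clinical sequelae resulting from lack of efficacy will be reported as AE if they fulfill the definition of an AE". The second is not: "Also, 'lack of efficacy' or 'failure of expected pharmacological action' constitutes an AE".

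The list of events that are not AEs, in the same section, includes "The disease/disorder being studied or expected progression, signs, or symptoms of the disease/disorder being studied, unless more severe than expected for the subject's condition". It also excludes anticipated day-to-day fluctuation of a pre-existing condition that does not worsen.

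On stopping treatment, Protocol 8.1 lists "Lack of efficacy from the intervention" beside, and apart from, an adverse event. SAP 7.4.1 does the same with "Lack of efficacy" among the primary reasons for discontinuation. Protocol 11.6 says "Withdrawal due to AEs should be distinguished from withdrawal due to other causes", and makes the AE definition the test.

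The safety endpoint in Protocol Table 3-1 is the number and percent of subjects with AEs or SAEs on treatment, split by relatedness. The overview in SAP 10.7.1.1 counts subjects with any TEAE, subjects who permanently stopped treatment because of a TEAE, and "the number of subjects with a TEAE related to study treatment". SAP 7.4.8 classes a TEAE as related for every recorded relationship except Not Related, so Unlikely and Unknown both count. SAP 10.7.1.2 tabulates TEAEs, serious TEAEs and related TEAEs by system organ class and preferred term.

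**The concern.** In a trial of a pain gel, non-response usually shows itself as knee pain that stays where it was. Protocol 11.1 gives a site grounds to enter that as an AE (the product did not work) and grounds not to (expected symptoms of the condition). Nothing in the protocol or SAP says which applies.

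The overview counts are what a reader will take as the tolerability of the gel. The study has one arm, so no control group offsets non-response recorded as an AE. The AE tables are shown by product, and products differ by country. A difference in recording habit between sites could therefore look like a difference between gels, even though no formal comparison is planned.

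**Working it through.** The documents state no expected AE rate and no non-response rate, so there is no figure to reproduce. The check is textual, followed by an illustration on assumed rates.

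**One subject, two compliant records.** Take a subject whose knee pain stays at its expected level, who tells the site the gel is not helping, and who stops using it.

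| Step | Site A | Site B |
|---|---|---|
| Protocol 11.1 | Applies the unconditional sentence: lack of efficacy entered as an AE | Applies the exclusion of expected symptoms: no AE entered |
| Protocol 11.6 and SAP 7.4.1 | The AE definition points to an AE withdrawal, yet a separate lack-of-efficacy reason is also available | Lack of efficacy |
| Any TEAE (SAP 10.7.1.1) | Counted | Not counted |
| Related TEAE (SAP 7.4.8) | Counted unless marked Not Related | Not counted |
| Discontinued due to a TEAE (SAP 7.4.8) | Counted if the action taken is drug withdrawn | Not counted |

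At Site A the subject can appear under lack of efficacy in the disposition table and as a TEAE discontinuation in the safety overview. The qualifier about symptoms worse than expected does not help, because this subject's symptoms are not worse.

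**Illustration.** Let h be the share of users with a harm-type AE and q the share with lack of efficacy recorded as an AE. Both are assumptions. The share with any AE is

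- 1 − (1 − h)(1 − q) if the two are independent;
- max(h, q) if one group lies inside the other;
- h + q if they do not overlap.

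With h = 5% and q = 10%: independent, 1 − 0.95 × 0.90 = 14.5%; nested, 10%; disjoint, 15%. The denominator is the safety population, meaning everyone who used the product at least once, so up to the roughly 195 enrolled. In subjects, 0.05 × 195 = 9.75 (about 10) becomes 0.145 × 195 = 28.3 (about 28).

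Over h from 2% to 10% and q from 5% to 30%, the independent figure runs from 6.9% to 37.0%. If lack of efficacy is never entered as an AE, the percentage stays at h.

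**Can the preferred-term tables undo this?** They give T, the subjects with any TEAE, and L, the subjects with the lack-of-efficacy term. They do not show how many subjects had that term alone. The count without it is therefore known only to lie between T − L and T. In the example above, T is about 28.3 and L is 0.10 × 195 = 19.5, so the range is about 9 to 28, around a harm-type count of about 10.

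**The case against.** The strongest reply is that Protocol 11.1 is not contradictory. It can be read as keeping expected knee pain out of the AE record while a report that the product failed goes in under that term. This stands: a reader might infer a flat contradiction, and the text does not force one. What it leaves open is when persisting pain becomes a report of product failure.

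Second, a reader might infer that lack-of-efficacy terms cannot be seen in the planned output. SAP 10.7.1.2 does not support that. A term coded as lack of efficacy would have its own preferred-term row in the TEAE and related-TEAE tables, and SAP 10.7.1.3 lists every AE. The overview rows are also described as not exhaustive, and the table shells are in a separate document. So the mixing is confined to the headline counts. Those cannot be recovered from the preferred-term tables, though they could be recounted by hand from the listing.

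Third, a separate discontinuation category is not itself inconsistent, because a subject can have an AE recorded and another primary reason for stopping. That also stands. The remaining difficulty is that Protocol 11.6 sorts withdrawals by a definition that itself includes lack of efficacy.

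Fourth, nothing turns an NRS or WOMAC score into an AE. Recording depends on subject report, open questioning and investigator assessment, so q may be far below the true non-response rate. Safety is descriptive and no efficacy analysis is touched. All of this is correct and limits the importance of the point.

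**Conclusion.** The point holds as a gap in classification with a one-directional effect. Where lack of efficacy is entered as an AE, the headline percentage of subjects with a TEAE can only stay the same or rise. The related count rises with it unless the event is marked Not Related. The discontinuation count rises where the action taken is drug withdrawn.

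The size is unknown. A reader might assume that 20% to 40% of users get no useful relief and apply this to the 147 expected completers, giving 29 to 59 extra subjects with AEs. The documents do not support that figure. The rate is not stated, it supposes that every non-responder is recorded and has no other AE, and AE percentages use the safety population rather than completers. The 14.5% illustration rests equally on assumed rates and shows only direction and scale.

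Nor do the documents support concluding that the safety results would be uninterpretable, since individual terms stay visible. Severity is minor. It is worth doing because it is a cheap improvement.

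**What to change.** In the protocol, reconcile the two lists in 11.1 with 8.1 and 11.6 so that one classification applies to a subject whose symptoms persist at the expected level. Which classification to adopt is for the sponsor. Reporting obligations need not change.

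In SAP 10.7.1.1, present three overview counts with and without lack-of-efficacy terms: subjects with at least one TEAE, subjects with a related TEAE, and subjects who stopped treatment because of a TEAE. List the preferred terms treated as lack of efficacy before database lock. If data collection is too far advanced for a protocol clarification to help, the SAP change alone still makes the headline percentages readable as tolerability.

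The cost is one clarification in the protocol and a few extra table rows.

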**Events NOT meeting the AE definition:**

- Any clinically significant abnormal laboratory findings (if applicable) or other abnormal safety assessments which are associated with the underlying disease, unless judged by the investigator to be more severe than expected for the subject's condition.
- The disease/disorder being studied or expected progression, signs, or symptoms of the disease/disorder being studied, unless more severe than expected for the subject's condition.
- Medical or surgical procedure (e.g. endoscopy, appendectomy) is not the AE. The condition that leads to the procedure is an AE (e.g. appendicitis).
- Situations where an untoward medical occurrence did not occur (social and/or convenience admission to a hospital).
- Anticipated day-to-day fluctuations of pre-existing disease(s) or condition(s) present or detected at the start of the study that do not worsen.

Property of Haleon - Confidential

May not be used, divulged, published or otherwise disclosed without the consent of  
 Haleon

Clinical Protocol Template, TMF-187821, v11.0. Parent SOP: **CCI**

## 11.2 Definition of a Serious Adverse Event (SAE)

A Serious Adverse Event (SAE) is a particular category of an adverse event where the adverse outcome is serious. If an event is not an AE per definition above, then it cannot be an SAE even if serious conditions are met (e.g. hospitalisation for signs/symptoms of the disease under study, death due to progression of disease).

A serious adverse event is any untoward medical occurrence at any dose that:

- **Results in death**
- **Is life-threatening**
  - The term 'life-threatening' in the definition of 'serious' refers to an event in which the subject was at risk of death at the time of the event. It does not refer to an event, which hypothetically might have caused death, if it were more severe;
- **Requires inpatient hospitalisation or prolongation of existing hospitalisation**
  - In general, hospitalisation signifies that the subject has been detained (usually involving at least an overnight stay) at the hospital or emergency ward for observation and/or treatment that would not have been appropriate in the physician's office or outpatient setting. Complications that occur during hospitalisation are AEs. If a complication prolongs hospitalisation or fulfils any other serious criteria, the event is serious. When in doubt as to whether "hospitalisation" occurred, or was necessary, the AE should be considered serious.
  - Hospitalisation for elective treatment of a pre-existing condition that did not worsen from baseline is not considered an AE.
- **Results in persistent or significant disability/incapacity**
  - The term disability means a substantial disruption of a person's ability to conduct normal life functions.
  - This definition is not intended to include experiences of relatively minor medical significance such as uncomplicated headache, nausea, vomiting, diarrhoea, influenza, and accidental trauma (e.g., sprained ankle) which may interfere with or prevent everyday life functions but do not constitute a substantial disruption
- **Results in congenital anomaly/birth defect**
- **Other situations:**
  - Medical or scientific judgment should be exercised in deciding whether SAE reporting is appropriate in other situations such as important medical events that may not be immediately life-threatening or result in death or hospitalisation but may jeopardize the subject or may require medical or surgical intervention to prevent one of the other outcomes listed in the above definition. These events should usually be considered serious.
  - Examples of such events include invasive or malignant cancers, intensive treatment in an emergency room or at home for allergic bronchospasm, blood

Property of Haleon - Confidential

May not be used, divulged, published or otherwise disclosed without the consent of  
 Haleon

Clinical Protocol Template, TMF-187821, v11.0. Parent SOP: **CCI**

dyscrasias or convulsions that do not result in hospitalisation, or development of drug dependency or drug abuse.

**Note:** Classification of an AE as 'serious' is based on the outcome of the event and is a factor in determining reporting requirements.

### 11.3 Reporting Procedures

The investigator is responsible for detecting, documenting, and reporting events that meet the definition of an AE and remain responsible for following up on AEs that are serious, considered related to the study product(s), participation in the study, or a study procedure, or that caused the subject to discontinue the study product or study.

Each AE is to be assessed to determine if it meets the criteria for a SAE. If an SAE occurs, expedited reporting will follow local and international regulations, as appropriate.

When an AE occurs, it is the responsibility of the investigator (or medically qualified designee) to review all documentation (e.g., hospital progress notes, laboratory, and diagnostics reports) related to the event.

The investigator or site staff will then record all relevant information regarding an AE in the eCRF and all details relating to an SAE in the paper SAE Form provided.

It is **not** acceptable for the investigator (or medically qualified designee) to send photocopies of the subject's medical records to Haleon in lieu of completion of the AE eCRF page/SAE form.

The investigator (or medically qualified designee) will attempt to establish a diagnosis of the event based on signs, symptoms, and/or other clinical information. The diagnosis will be the documented as the AE/SAE where known and not the individual signs/symptoms. (e.g., upper respiratory tract infection, seasonal allergy, etc. instead of runny nose).

AEs elicited by the investigator (or medically qualified designee) in a standard manner at the study visits should also be recorded in the AE section of the eCRF and/or using the SAE form (subject to the classification of the AE). Care will be taken not to introduce bias when questioning a subject about any changes in their health. Open-ended and non-leading verbal questioning should be used.

#### 11.3.1 Reporting of an Adverse Event

All AEs will be reported on the AE page of the eCRF by the investigator or site staff. It should be noted that the form for collection of SAE information is not the same as the AE eCRF. Where the same data are collected, the AE eCRF page and the SAE form must be completed in a consistent manner. For example, the same AE term should be used on both. AEs should be reported using concise medical terminology on the eCRF as well as on the form for collection of SAE information.

Property of Haleon - Confidential

May not be used, divulged, published or otherwise disclosed without the consent of  
 Haleon

Clinical Protocol Template, TMF-187821, v11.0. Parent SOP: **CCI**

### 11.3.2 Reporting of a Serious Adverse Event

In addition to recording the details of each AE on the AE eCRF page, an SAE form should be completed, as fully as possible. Hard copies of the 'paper' SAE form will be provided in the investigator study master file. Original SAE forms will be retained in the investigator study master file.

It is essential to enter the following information:

- Protocol and subject identifiers
- Subject demography
- Description of events, with diagnosis if available
- Investigator opinion of relationship to study product (or study procedure, if appropriate)
- Criterion for seriousness.

The following are desirable and are of particular relevance for investigator and Haleon assessment of the SAE report:

- Date of onset of AE
- Date AE stopped, if relevant
- Study product start date
- Study product end date if relevant
- Action taken in relation to the study product
- Outcome if known

The SAE form, completed as fully as possible, must be scanned and e-mailed to the Single Case Processing mailbox ([Table 11-1](#)), with a copy to the appropriate Haleon or **CCI** Study Manager, with the study number and subject number in the subject line of the email **immediately and under no circumstance should this exceed 24 hours** after study site personnel learn of the event. The investigator will submit any updated SAE data to the sponsor, **immediately and under no circumstance should this exceed 24 hours** of it being available.

The initial report will be followed up with more information as relevant, or as requested by the study manager.

The Haleon Study Manager will be responsible for forwarding the SAE form to other Haleon personnel as appropriate.

The investigator (s) will be responsible for notifying the IRB/IEC of SAEs that occur during the study.

Property of Haleon - Confidential

May not be used, divulged, published or otherwise disclosed without the consent of  
 Haleon

Clinical Protocol Template, TMF-187821, v11.0. Parent SOP: **CCI**

## 11.4 Evaluating Adverse Events

### 11.4.1 Assessment of Intensity

The investigator will make an assessment of intensity for each AE reported during the study and will assign it to one of the following categories:

- Mild: An event that is easily tolerated by the subject, causing minimal discomfort and not interfering with everyday activities.
- Moderate: An event that is sufficiently discomforting to interfere with normal everyday activities
- Severe: An event that prevents normal everyday activities.

NOTE: An AE that is assessed as severe should not be confused with an SAE. Severe is a category utilized for rating the intensity of an event; and both non-serious AEs and SAEs can be assessed as severe. For example, a headache may be severe (interferes significantly with the subject's usual function) but would not be classified as serious unless it met one of the criteria for SAEs, listed above. An event is defined as 'serious' when it meets at least 1 of the predefined seriousness criteria as described in the definition of an SAE, NOT when it is rated as severe.

### 11.4.2 Assessment of Causality

The causality assessment is one of the criteria used when determining regulatory reporting requirements.

For each AE (serious and non-serious), the investigator (or medically qualified designee) **must** provide an assessment of causality on the AE eCRF page and the SAE form (subject to the classification of the AE). The investigator will also document in the medical notes that he/she has reviewed the AE and assessed causality, where applicable.

Property of Haleon - Confidential

May not be used, divulged, published or otherwise disclosed without the consent of  
 Haleon

Clinical Protocol Template, TMF-187821, v11.0. Parent SOP: **CCI**

A “reasonable possibility” of a relationship conveys that there are facts, evidence, and/or arguments to suggest a causal relationship, rather than a relationship cannot be ruled out. Generally, the facts (evidence) or arguments to suggest a causal relationship should be provided.

The investigator will use clinical judgment to determine the relationship and will also consult the Investigator Brochure (IB), Safety Statement and/or Product Information, for marketed products, in the determination of his/her assessment. Alternative causes, such as underlying disease(s), concomitant therapy, other risk factors, and the temporal relationship of the event to the study product will be considered and investigated.

For each AE/SAE, the investigator must document in the medical notes that he/she has reviewed the AE/SAE and has provided an assessment of causality.

The investigator’s assessment of causality must be provided for all AEs (serious and non-serious); the investigator must record the causal relationship in the eCRF, as appropriate, and report such an assessment in accordance with the SAE reporting requirements if applicable.

There may be situations when an SAE has occurred, and the investigator has minimal information to include in the initial report to Haleon. **However, it is very important that the investigator always make an assessment of causality for every event prior to the initial transmission of the SAE data to Haleon.** The investigator may change his/her opinion of causality in light of follow-up information and send an SAE follow-up report with the updated causality assessment.

